#### 11.1.5.2. Sample Size

The sample size estimate was obtained using the normal approximation to the binomial distribution and verified through simulations based on Kaplan-Meier methodology. The following assumptions were used in the sample size calculation:

Assumptions	Primary Effectiveness at 12 Months
Expected rate	60%
Performance goal	50%
Attrition (per year)	10%
Significance level (one-sided)	2.5%

Power	90%
Sample size	288

Under the hypothesis and assumptions outlined above, the required sample size for this endpoint analysis is 288 subjects treated with the IntellaNav StablePoint Catheter.

The expected rate for the primary effectiveness endpoint at 12 months was determined based on Boston Scientific's ZERO AF study data. The performance goal for the primary effectiveness endpoint at 12 months is the 2017 HRS Consensus Document recommended performance goal.

#### 11.1.5.3. Statistical Methods

For the analysis of the primary effectiveness endpoint at 12 months, the Kaplan-Meier (KM) 12-month (365-day) primary effectiveness event-free rate will be calculated. Event-free subjects who withdraw from the study or die prior to 12 months due to a device or procedure related adverse event will be considered to have an endpoint event at the time of study exit. Subjects who withdraw from the study or die prior to 12 months without experiencing an event will be censored on the date of their last study visit or arrhythmia/event monitor use, whichever is later. The 97.5% one-sided lower confidence limit of the observed 12-month primary effectiveness event-free rate will be compared to the performance goal of 50%. The lower confidence limit will be calculated as the pointwise confidence limit using the log-log methodology. If the lower confidence limit is greater than the performance goal, the null hypothesis will be rejected.

## 11.2. Secondary Endpoints

Secondary endpoint analyses will be performed after study completion and will be exploratory in nature. These endpoints have no powered hypotheses, and no alpha adjustment for multiple testing will be made.

## 11.2.1. Secondary Safety Endpoint: SAE and AE Rates

The secondary safety endpoint will evaluate the rate of Serious Adverse Events (SAE) and Adverse Events (AE) related to the procedure and/or study device through 12 months post Index Procedure

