# 6.4. Primary Safety Endpoint at 12 Months

The primary safety endpoint at 12 months is defined as the safety event-free rate at 12 months post-procedure.

Primary safety events will consist of a composite of the following serious procedure-related and/or device-related adverse events.

The following events will be counted through 7 days post index procedure or hospital discharge, whichever is later:

- Death
- Myocardial infarction (MI)
- Vagal Nerve Injury/Gastroparesis
- Transient ischemic attack (TIA)
- Stroke/Cerebrovascular accident (CVA)
- Thromboembolism
- Pericarditis
- Pneumothorax
- Major vascular access complications
- Pulmonary edema/heart failure

AV block\*

The following events will be counted through 30 days post index procedure:

Cardiac tamponade/perforation

And the following events will be counted through 12 months post index procedure:

- Atrial esophageal fistula
- Severe pulmonary vein stenosis (≥70% reduction in the diameter of the PV or PV branch from baseline)
- Persistent phrenic nerve palsy\*\*
- \* AV block not attributable to medication effect or vasovagal reaction.
- \*\*A non-recovered phrenic nerve palsy at 12 months post index procedure will count as a chronic primary endpoint. The study will collect information on phrenic nerve palsy observed before the end of the index procedure and, in case it occurred, will track information for potential recovery during the study visits.

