# 6.7. Secondary Endpoints

Secondary Endpoints include the following:

- Secondary Safety Endpoint SAE and AE Rates
- Secondary Effectiveness Endpoint 1 New or Increased Dose of AAD
- Secondary Effectiveness Endpoint 2 Single Procedure Success defined as freedom from primary effectiveness failure without a repeat procedure
- Secondary Effectiveness Endpoint 3 Symptomatic Recurrence: freedom from documented symptomatic AF/AT/AFL recurrence

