Evaluate the effectiveness of the StablePoint Catheter, assessed initially at 6 months, with a potential evaluation at 12 months if the 6-month analysis is not passed.	Failure free rate including failure to achieve success at index or repeated procedure in blanking period, more than one repeated procedure during blanking period, documented AF/AT or new onset AFL or interventions to treat these arrhythmias after blanking period, including repeated procedures cardioversion or pharmacologic treatment.  Effectiveness will be evaluated at a sixmonth analysis. If the 6-month analysis is not passed, an additional evaluation of primary effectiveness will be done at twelve months.	The effectiveness endpoint and the performance goal at 12 months were established based on the recommendations available in the 2017 HRS expert consensus statement on catheter and surgical ablation of atrial fibrillation.  The expected rates for both the 6- and 12-month Primary Effectiveness endpoints was determined based on Boston Scientific's ZERO AF study data. The 6-month Primary Effectiveness endpoint performance goal was determined by the meta-analysis of pivotal and IDE studies on AF ablation (section 11.1.2.2)								

		Page 45 of 129				
Evaluate the 12-months safety of the StablePoint Catheter	The primary safety endpoint is defined as the safety event-free rate at 12 months post-procedure.	The list of events contributing to the primary safety endpoints was selected from those typically associate with catheter ablation of AF.				
Evaluate the 12-months effectiveness of the StablePoint Catheter	Failure free rate including failure to achieve success at index or repeated procedure in blanking period, more than one repeated procedure during blanking period, documented AF/AT or new onset AFL or interventions to treat these arrhythmias after blanking period, including repeated procedures cardioversion or pharmacologic treatment.	The effectiveness endpoint and the performance goal at 12 months were established based on the recommendations available in the 2017 HRS expert consensus statement on catheter and surgical ablation of atrial fibrillation.				
	Secondary Endpoin	ts				
Adverse events reporting	SAE and AE Rates	Complete overview of the safety events collected in the study				
Anti-arrhythmic treatment	New or Increased Dose of AAD	This is an analysis of a component of the primary effectiveness endpoint				

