# 19. Safety Reporting

# 19.1. Reportable Events by investigational site to Boston Scientific

It is the responsibility of the investigator to assess and report to BSC any event which occurs in any of following categories of reportable events:

- All Serious Adverse Events
- All IntellaNav StablePoint Catheter and Force Sensing System Device Related Adverse Events
- All AEs associated with BSC commercialized devices
- All Procedure Related AEs
- All Thromboembolic Events
- All Device Deficiencies related to the BSC study device
- Unanticipated Adverse Device Effects/Unanticipated Serious Adverse Device Effects previously not defined in the IFU and ICF
- New findings/updates in relation to already reported events

Whenever possible, the medical diagnosis should be reported as the Event Term instead of individual symptoms. If it is unclear if an event fits one of the above categories, or if the

event cannot be isolated from the device or procedure, it should be submitted as an adverse event and/or device deficiency.

The following clinical events will not be considered adverse events for this clinical study:

- Pre-existing diseases or conditions (including AFib, AFI, AT) will not be reported as
  adverse events unless there has been a substantial increase in severity or frequency of
  the problem as compared to the subject's baseline which cannot be attributed to the
  expected progression of the disease or condition.
- Pre-planned hospitalizations at time of enrollment or for a pre-existing condition.
- AF episodes with medical intervention or hospitalization due to arrhythmia recurrence during the blanking period (Index Procedure to 3 Month Follow-Up).

Death should not be recorded as an AE, but it should be reflected as an outcome of one (1) specific SAE (see Table 19-1 for AE definitions).

The Boston Scientific Medical Safety group will provide safety oversight by reviewing and classifying individual events reported to the sponsor. Routine aggregate safety reviews will be conducted to ensure subject safety.

If an additional ablation procedure is required, this additional ablation procedure should only be considered an Adverse Event if it is associated with subject worsening condition or a new diagnosis. The ablation would be considered a corrective action.

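### Section 11.2.1, on its natural reading, limits the secondary safety endpoint to events rated related, in conflict with Table 6-2 and with the all-SAE collection rule

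*Combined protocol and SAP*

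**What the plan says.** The endpoint list in Section 6.7 names the secondary safety endpoint "SAE and AE Rates", with no limit by relatedness. Table 6-2 in Section 6.8 gives its justification as "Complete overview of the safety events collected in the study". The analysis definition in Section 11.2.1 is "the rate of Serious Adverse Events (SAE) and Adverse Events (AE) related to the procedure and/or study device through 12 months post" procedure.

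Collection is wider. Section 19.1 lists "All Serious Adverse Events" and "All Thromboembolic Events" as reportable without reference to cause. Non-serious events are reportable mainly where they are tied to the procedure or a device (for example "All Procedure Related AEs").

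The 12-month primary safety endpoint in Section 6.4 is a "composite of the following serious procedure-related and/or device-related adverse events", and the 30-day endpoint in Section 6.1 is limited in the same way. Section 11.2 makes all secondary analyses exploratory, with no powered hypotheses.

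**The concern.** Three parts of the plan describe the scope of one endpoint differently. The name and the justification are unrestricted, the collection rule takes in every SAE, and the analysis sentence appears to keep only the related ones. A statistician programming from Section 11.2.1 would filter on relatedness, and the result would not be the overview that Table 6-2 describes.

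This matters because of the design. The trial has one arm and no control device, so raters know the treatment and no comparator rate can test their relatedness judgments. A count of all SAEs does not depend on those judgments; a count of related SAEs does. The related events are a subset of all events, so a related-only table can never show more events than the full one. Any error from the restriction therefore makes the 12-month safety profile look more favourable.

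**Working it through.** There is no stated figure to reproduce and no calculation to run: the endpoint is descriptive, and its scope touches no alpha, power or sample size. The check is to follow an SAE rated unrelated through each place where the supplied text plans a summary.

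| Place | Scope | Shows an SAE rated unrelated? |
|---|---|---|
| Section 6.1, 30-day primary safety | Serious related events; death, stroke and thromboembolism to day 7 or discharge, whichever is later | No |
| Section 6.4, 12-month primary safety | Serious related events; the same limit for death, stroke and thromboembolism; fistula, severe PV stenosis and persistent phrenic nerve palsy to 12 months | No |
| Section 11.2.1, secondary safety | Related SAEs and AEs to 12 months, on the natural reading | No |
| Sections 11.1.3.3 and 11.1.5.3, effectiveness | Deaths from a device- or procedure-related adverse event count as failures; other event-free deaths are censored | No |
| Sections 6.8 and 11.4.5, freedom from cardiovascular hospitalization | No relatedness limit; not defined further in the supplied text | Only if it led to a cardiovascular admission |

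Three steps follow from the table.

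1. **Late events.** After day 7 or discharge, neither primary composite counts a death, stroke or thromboembolic event, related or not. From then to 12 months, Section 11.2.1 is the only safety endpoint that could show one.

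2. **Deaths.** Section 19.1 has death recorded as the outcome of an SAE, not as an adverse event in its own right. If the SAE summary keeps only related events, a death whose SAE is rated unrelated has no row in it. The 12-month effectiveness rule is "Subjects who withdraw from the study or die prior to 12 months without experiencing an event will be censored", so that analysis does not show the death as an event either.

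3. **The grammar of Section 11.2.1.** The sentence allows two readings.
   - *Related to* qualifies both SAEs and AEs. This is the natural reading: one rate governs the pair, and the time window that follows clearly applies to both members, so the phrase just before it should too.
   - *Related to* qualifies only AEs, giving all SAEs plus related AEs. SAEs rated unrelated would then be included, with deaths as their outcomes. A non-serious thromboembolic event rated unrelated would still be collected under Section 19.1 and left out of the endpoint.

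Only the second reading comes close to Table 6-2 and Section 19.1, and the text does not say that it is the one meant.

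**The case against.** The strongest reply is that this may be loose syntax and not a plan to omit SAEs. The second reading is grammatically possible and fits the unrestricted endpoint name. That point stands, and it is why the finding is stated for the natural reading. It is also a reason to reword, because a definition that can be programmed in two ways should not be left as it is.

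Other points on that side:

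- **Cardiovascular hospitalization is not limited by relatedness.** This stands. It would capture some strokes and cardiac SAEs rated unrelated, depending on a definition not given. It would not show non-cardiovascular SAEs or deaths without admission.
- **The list of additional analyses is open, and Section 11.4.5 refers to a Statistical Analysis Plan for detail.** This stands as a limit: that further detail is not in the supplied text, so absence can be claimed only for what is supplied. The conflict between Table 6-2 and Section 11.2.1 remains in any case.
- **Relatedness is not unchecked.** Table 19-2 classes events that cannot be assessed as possibly related, which shrinks the unrelated group. Section 21.3 has the DMC oversee all adverse events. Section 19.7 sends subject deaths to the CEC, although Section 21.2 names only deaths that may be related. These are real safeguards, but they are oversight and specify no reported analysis.
- **Deaths appear in subject accountability.** Section 9.3 requires every enrolled subject to be accounted for and names death as a withdrawal reason. That is a disposition record, not a safety summary.
- **The endpoint is exploratory, and the Table 6-2 phrase is a justification.** Both are true. They lower the weight of the point without removing the inconsistency.

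A reader might go further and infer that deaths, strokes and SAEs rated unrelated have no planned analysis of any kind. The documents do not support that, given the hospitalization endpoint, the open list and the further detail not supplied.

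**Conclusion.** The point holds in this form: on its natural reading, Section 11.2.1 restricts the secondary safety endpoint to procedure- or device-related events, in conflict with Table 6-2 and with the collection rule in Section 19.1. Apart from freedom from cardiovascular hospitalization, the supplied text specifies no summary of SAEs, deaths, strokes or thromboembolic events regardless of relatedness.

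The size is one of scope, not of a number. The documents give no all-cause SAE rate and nothing from which to derive one, so any count of affected subjects would be a guess, and the finding does not need it. No success criterion in Section 6.6 uses this endpoint, so no pass-or-fail decision changes. What changes is the completeness of the reported 12-month safety profile.

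The conclusion rests on two assumptions: that the relatedness phrase applies to both SAEs and AEs, and that no text outside the supplied document adds the missing summaries. The change should be made, and it is a modest one.

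**What to change.** Reword Section 11.2.1 so that the endpoint reports two things through 12 months after the index procedure:

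- (a) all SAEs, all deaths and all thromboembolic events, regardless of relatedness;
- (b) procedure- or device-related SAEs and AEs, as a subset.

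State the population as ATTEMPT and TREATMENT subjects, which matches Section 11.3.1, with ATTEMPT subjects contributing to 30 days, which matches Section 9.5.3. Tabulation by onset period is optional.

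The cost is one reworded definition and a few extra descriptive tables. Section 19.1 already requires the data, so nothing new is collected. Alpha, power and sample size do not change.

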#### 11.2.2. Secondary Effectiveness Endpoint 1: New or Increased Dose of AAD

The first secondary effectiveness endpoint will evaluate the 12-month effectiveness rate when considering only newly prescribed or increased dosages of previously prescribed AADs as endpoint failures.

For this analysis endpoint events will be defined as:

- Acute procedural failure
- Use of non-study ablation catheter in the index procedure or in a repeat procedure during the blanking period
- More than one repeat procedure during the blanking period (90 days post index procedure)
- Documented atrial fibrillation, or new onset of atrial flutter or atrial tachycardia between 91 days and 365 days post index procedure captured by one of the following methods:
  - ≥ 30 seconds in duration from the study specific event monitor or Holter Monitor
  - ≥ 10 seconds 12-lead Electrocardiography (ECG)
- Any of the following interventions for atrial fibrillation, or new onset of atrial flutter or atrial tachycardia between 91 days and 365 days post index procedure:
  - Repeat procedure
  - Electrical and/or pharmacological cardioversion
  - Prescribed a new AAD\*
  - Prescribed an increased dose of a previously failed AAD\*

# 11.2.3. Secondary Effectiveness Endpoint 2: Single Procedure Success

The second secondary effectiveness endpoint will evaluate the 12-month effectiveness rate when considering only subjects who do not require a repeat procedure within the blanking period as a success.

For this analysis endpoint events will be defined as:

- Acute procedural failure
- A repeat procedure during the blanking period (90 days post index procedure)
- Documented atrial fibrillation, or new onset of atrial flutter or atrial tachycardia between 91 days and 183\* days post index procedure captured by one of the following methods:
  - ≥ 30 seconds in duration from the study specific event monitor or Holter Monitor
  - ≥ 10 seconds 12-lead Electrocardiography (ECG)

\*AADs for endpoint will consist of all Class I/III, including Amiodarone, and any Class II/IV medications taken for control of atrial fibrillation (AF)/Atrial tachycardia (AT)/Atrial flutter (AFL)

- Any of the following interventions for atrial fibrillation, or new onset of atrial flutter or atrial tachycardia between 91 days and 365 days post index procedure:
  - Repeat procedure
  - Electrical and/or pharmacological cardioversion
  - Prescribed any AAD\*

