## Primary Effectiveness Endpoint at 6 Months

This primary effectiveness endpoint at 6 months is defined as the primary effectiveness event-free rate at 6 months post-procedure.

Primary effectiveness events determining a failure are defined as:

- Acute procedural failure
- Use of amiodarone post index procedure
- Use of non-study ablation catheter in the index procedure or in a repeat procedure during the blanking period
- More than one repeat procedure during the blanking period (90) days post index procedure)
- Surgical ablation of Atrial Fibrillation (AF)/Atrial Tachycardia (AT)/Atrial Flutter (AFL) post index procedure
- Documented atrial fibrillation, or new onset of atrial flutter or atrial tachycardia between 91 days and 183\* days post index procedure captured by one of the following methods:

\*\*A non-recovered phrenic nerve palsy at 12 months occurring post index procedure will count as a chronic primary endpoint. The study will collect information on phrenic nerve palsy observed before the end of the index procedure and, in case of occurrence, will track information for potential recovery during the study visits.

Clinical Eva	aluation of the StablePoint Catheter and Force-Sensing System				
for Paroxysmal A trial F ibrillation					
	(NEWTON AF)				
	
 
≥ 30 seconds in duration recording from the study specific event monitor or Holter Monitor
 
				
	
 
≥ 10 seconds 12-lead Electrocardiography (ECG)
 
				
	
 
Any of the following interventions for atrial fibrillation, or new onset of atrial flutter or atrial tachycardia between 91 days and 183* days post index procedure:
 
				
	Repeat procedure				
	Electrical and/or pharmacological cardioversion				
	Prescribed any AAD**				
	*If evaluating the primary effectiveness endpoint at 12 months, then primary effectiveness events will include events seen through 365 days post index procedure.				
	**AADs for endpoint will consist of all Class I/III, including Amiodarone, and any Class II/IV medications taken for control of atrial fibrillation (AF)/Atrial tachycardia (AT)/Atrial flutter (AFL) recurrence.				
	Primary Effectiveness Endpoint at 12 Months				
	This primary effectiveness endpoint at 12 months is defined as the primary effectiveness event-free rate at 12 months post-procedure.				
Secondary Endpoints	Secondary Endpoints include the following:				

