# 6.5. Primary Effectiveness Endpoint at 12 Months

The primary effectiveness endpoint at 12 months is defined as the event-free rate at 12 months (365 days) post-procedure.

Primary effectiveness events at 12 months are defined as:

- Acute procedural failure
  - Failure to achieve acute procedural success in the index procedure or in a repeat procedure during the blanking period.
  - Acute procedural success is defined as the achievement of electrical isolation of all PVs using the StablePoint catheter only. Electrical isolation of a PV is demonstrated by entrance block after 20 minutes waiting period. If exit block testing is performed, the PV will only be considered as isolated if both entrance and exit block testing are successful.
- Use of amiodarone post index procedure
- Use of non-study ablation catheter in the index procedure or in a repeat procedure during the blanking period.
- More than one repeat procedure during the blanking period (90 days post index procedure)
- Surgical ablation of Atrial Fibrillation (AF)/Atrial Tachycardia (AT)/Atrial Flutter (AFL) post index procedure
- Documented atrial fibrillation, or new onset of atrial flutter or atrial tachycardia between 91 days and 365 days post index procedure captured by one of the following methods:
  - ≥ 30 seconds in duration from the study specific event monitor or Holter Monitor

- ≥ 10 second 12-lead Electrocardiography (ECG)
- Any of the following interventions for atrial fibrillation, or new onset of atrial flutter or atrial tachycardia between 91 days and 365 days post index procedure:
  - Repeat procedure
  - Electrical and/or pharmacological cardioversion
  - Prescribed any AAD\*

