# 11.2.4. Secondary Effectiveness Endpoint 3: Symptomatic Recurrence

The third secondary effectiveness endpoint will evaluate the 12-month effectiveness rate when considering only documented symptomatic arrhythmia recurrences or interventions for arrhythmias as endpoint failures.

For this analysis endpoint events will be defined as:

- Acute procedural failure
- Use of non-study ablation catheter in the index procedure or in a repeat procedure during the blanking period
- More than one repeat procedure during the blanking period (90 days post index procedure)
- Documented symptomatic atrial fibrillation, or new onset of symptomatic atrial flutter or symptomatic atrial tachycardia between 91 days and 365 days post index procedure captured by one of the following methods:
  - ≥ 30 seconds in duration from the study specific event monitor or Holter Monitor
  - ≥ 10 seconds 12-lead Electrocardiography (ECG)
- Any of the following interventions for atrial fibrillation, or new onset of atrial flutter or atrial tachycardia between 91 days and 365 days post index procedure:
  - Repeat procedure
  - Electrical and/or pharmacological cardioversion
  - Prescribed any AAD\*
- \*AADs for endpoint will consist of all Class I/III, including Amiodarone, and any Class II/IV medications taken for control of atrial fibrillation (AF)/Atrial tachycardia (AT)/Atrial flutter (AFL) recurrence.

\*AADs for endpoint will consist of all Class I/III, including Amiodarone, and any Class II/IV medications taken for control of atrial fibrillation (AF)/Atrial tachycardia (AT)/Atrial flutter (AFL) recurrence.

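### As written, the 12-month Single Procedure Success endpoint stops counting documented recurrences at day 183, although its own intervention item and the other 12-month endpoints run to day 365

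*Combined protocol and SAP*

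**What the plan says.** Section 11.2.3 sets the horizon: "The second secondary effectiveness endpoint will evaluate the 12-month effectiveness rate". Two components of the event list then carry different end dates. Documented arrhythmia is worded "Documented atrial fibrillation, or new onset of atrial flutter or atrial tachycardia between 91 days and 183", the 183 bearing an asterisk. The intervention component is worded "Any of the following interventions for atrial fibrillation, or new onset of atrial flutter or atrial tachycardia between 91 days and 365 days".

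Section 6.7 gives the short definition: "Single Procedure Success defined as freedom from primary effectiveness failure without a repeat procedure". The 12-month primary endpoint in Section 6.5 counts "Documented atrial fibrillation, or new onset of atrial flutter or atrial tachycardia between 91 days and 365 days post index procedure". Section 11.2.2 uses the same window, and Section 11.2.4 uses it for symptomatic recurrence: "Documented symptomatic atrial fibrillation, or new onset of symptomatic atrial flutter or symptomatic atrial tachycardia between 91 days and 365 days post index procedure".

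An asterisked 183 also appears in the synopsis text for the 6-month primary endpoint, where its note says: "If evaluating the primary effectiveness endpoint at 12 months, then primary effectiveness events will include events seen through 365 days post index procedure". The entry for primary effectiveness failure in Section 26.2 has an equivalent note. Both notes are worded for primary effectiveness. The notes printed around Section 11.2.3 only define which antiarrhythmic drugs count.

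**The concern.** By Section 6.7, single-procedure success is primary success with an extra condition, so every single-procedure success should also be a primary success. The event list in Section 11.2.3 breaks that. A subject with AF on an event-monitor recording at day 300, and no antiarrhythmic drug, cardioversion or repeat procedure, fails the 12-month primary endpoint yet counts as a single-procedure success. The endpoint meant to be stricter could report the higher rate.

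The error favours the device, and two analysts working from different sections could report different rates from the same data.

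A smaller mismatch lies beside it: the list does not reproduce every component of Section 6.5, so it falls short of Section 6.7 even once the window is corrected.

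**Working it through.** The plan states no expected rate, power or sample size for this endpoint, so there is no design figure to reproduce. The check compares event windows and then sizes the difference.

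**1. Windows for documented AF, or new AFL or AT**

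| Endpoint | Section | Horizon | Last day counted |
|---|---|---|---|
| Primary effectiveness, 6 months | 6.3 | 6 months | 183 |
| Primary effectiveness, 12 months | 6.5 | 12 months | 365 |
| Secondary effectiveness 1 | 11.2.2 | 12 months | 365 |
| Secondary effectiveness 2 (single procedure) | 11.2.3 | 12 months | 183, asterisked |
| Secondary effectiveness 3 | 11.2.4 | 12 months | 365 |

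Section 11.2.3 is the only 12-month endpoint with the 6-month window, and it conflicts with its own intervention item (day 365).

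**2. Follow-up ignored by the literal reading**

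- Evaluation window, days 91 to 365: 365 − 91 + 1 = 275 days.
- Part without rhythm-based failures, days 184 to 365: 365 − 184 + 1 = 182 days.
- Share: 182 / 275 = 66%.
- Minimum event-monitor transmissions (two per month after the 3-month visit, Section 13.4.1): 2 × 9 = 18 for months 4 to 12, of which 2 × 6 = 12 fall in months 7 to 12.
- The 12-month Holter and ECG are also ignored. The 6-month visit may fall as late as day 180 + 30 = 210 (Section 10.6.6), so a 6-month Holter recorded after day 183 would be ignored too.

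**3. Possible effect on the rate**

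The documents give no single-procedure rates. As a proxy, take the planning event-free rates of the primary endpoints: 72% at 6 months (Section 11.1.3.2) and 60% at 12 months (Section 11.1.5.2).

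- Failures after day 183: 72% − 60% = 12 points; 0.12 × 299 = 35.9, about 36 subjects.
- Let s be the share of these that are documented recurrences with no counted intervention by day 365. The plan does not give s, so it is varied over its full range. Literal rate = 60% + s × 12 points.

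| s | Literal rate | Extra successes of 299 |
|---|---|---|
| 0 | 60% | 0 |
| 25% | 63% | 9 |
| 50% | 66% | 18 |
| 75% | 69% | 27 |
| 100% | 72% | 36 |

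**4. Event list against Section 6.5**

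Most primary components are still caught. Acute procedural failure covers PV isolation achieved with another catheter, any blanking-period repeat counts, and any counted antiarrhythmic drug prescribed for AF, or new AFL or AT, in days 91 to 365 counts. Three are not:

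- amiodarone use confined to the blanking period;
- use of a non-study catheter at the index procedure for something other than PV isolation;
- surgical ablation, if it is not classed as a repeat procedure.

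**The case against.** The strongest reply is that the intended window is evident. Section 6.7 ties the endpoint to primary effectiveness failure, Section 26.2 defines that term with a note extending 183 to 365 days at twelve months, and Section 11.2.3 itself speaks of a 12-month rate. On this view a footnote was simply not repeated. The footnotes in this part of the text may also have been displaced when it was read from PDF. The probable intent is conceded: the asterisk looks carried over from the primary endpoint. But Section 11.2.3 is the detailed event list an analyst would program from, no rule says Section 6.7 overrides it, and the notes that extend the window are worded for the primary endpoint.

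On size, the 12-point figure comes from a different endpoint and is not a strict bound, because the observed late-failure rate could differ. Some late failures will also have a counted intervention, or belong to subjects who already fail through a blanking-period repeat. The upper end is therefore unlikely.

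The residual gaps are also narrow. Amiodarone is barred after the procedure and the study catheter is mandatory for additional ablations, so those two arise only through deviations. Section 26.2 further limits the non-study-catheter item to AF targets, although Section 6.5 does not. Endpoints 1 and 3 likewise lack stand-alone amiodarone and surgical-ablation items, so that omission may be deliberate. These points reduce the weight of the gaps but leave the window error untouched.

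**Conclusion.** The concern holds. The event list in Section 11.2.3, followed as written, gives a 12-month endpoint a 6-month window for documented recurrence and can classify a 12-month primary failure as a single-procedure success. The overstatement is between 0 and about 12 percentage points (up to about 36 of 299 subjects). That range assumes the primary planning rates are a fair proxy and leaves the share of late failures without a counted intervention open. It is zero if the day-365 reading is applied or if every late failure also has a counted intervention.

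The consequence is limited. Section 11.2 says: "Secondary endpoint analyses will be performed after study completion and will be exploratory in nature". The endpoint enters none of the success criteria in Section 6.6, so primary conclusions, type I error and sample size do not change. It should still be corrected, because a named secondary effectiveness endpoint currently has two possible values from the same data and the literal one is favourable.

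**What to change.** In Section 11.2.3, replace the asterisked 183 with 365. Define the endpoint events as all Section 6.5 events through day 365, plus any repeat procedure during the blanking period. This restores the relation stated in Section 6.7 and closes the three residual gaps. Separately, confirm whether leaving stand-alone amiodarone and surgical-ablation items out of Secondary Effectiveness Endpoints 1 and 3 is intended.

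The cost is one edit to an exploratory endpoint definition, documented in an amended Statistical Analysis Plan before the analysis, as Section 11.4.6 requires. Rhythm monitoring already runs to 12 months, so no further data collection is needed. Compared with the literal reading, the reported rate will stay the same or fall.
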